### 5.2.1 XL888 dose levels

Open label phase I trial. Primary objective is to determine the recommended phase 2 dose (RP2D) of the combination of XL-888 and Pembrolizumab in a broad spectrum of GI tumors. The design is 3+3 with 3 dose levels of XL888 (X).

Dose level	XL-888	Pembrolizumab
1 days	45 mg PO twice weekly (Days 1 and 4)	200 mg IV every 21
2 days	90 mg PO twice weekly (Days 1 and 4)	200 mg IV every 21
3 every 21 days	60 mg PO twice weekly (Days 1 and 4)	200 mg IV

**Dose level 3 will only be tested if we observe 2 DLT's on dose level 2.**

### 5.2.2 Dose Escalation

Starting dose of 45mg; if  $\geq 2$  patients with DLTs in 3 ( $\geq 2/3$ ) or 6 ( $\geq 2/6$ ) subjects; stop and consider reduced dose of XL888. If not, increase dose to 90 mg and test 3-6 patients. If  $\geq 2$  patients with DLTs in 3 or 6 subjects, reduce dose to 60 mg and try again. If an acceptable dose is identified, treat 16 more patients at the MTD. Prior to dose escalation, we will obtain approval from the Data Safety and Monitoring Committee (DSMC).

**5.2.3 Dose limiting toxicity (DLT)** will be defined as any of the following definitely treatment related adverse events during the first 21 days of therapy:

- Grade IV neutropenia lasting more than 8 days; any neutropenic fever or sepsis;
- Grade III with clinically significant bleeding or any grade IV thrombocytopenia;
- Grade III nausea, vomiting, or diarrhea, lasting  $>72$  hours despite adequate supportive care;
- Other non-hematologic treatment-related toxicity at Grade III or higher
- Grade 4 asymptomatic laboratory abnormalities that last for more than 24 hours or Grade 3 asymptomatic laboratory abnormalities lasting more than 21 days is a DLT.
- Grade IV or higher diarrhea, nausea, vomiting
- In ability to take more than 75% of XL888 due to toxicity.

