## 2.0 TRIAL DESIGN

Open label phase I trial. Primary objective is to determine the recommended phase 2 dose (RP2D) of the combination of XL888 and pembrolizumab. The design is 3+3 with 3 dose levels of XL888 (X). MTD is defined as the dose at which less than one-third of the subjects experience a DLT in the first 4 weeks of treatment.

After determining the RP2D, an additional 16 patients with pancreatic cancer (Arm A) and 16 patients with colorectal cancer (Arm B) will be enrolled in an expansion phase to confirm toxicity profile and obtain paired biopsies. Paired biopsy performed on 8 patients in each group. Patient selected for biopsy must have a primary or metastatic non-bone site that is amenable to safe biopsy. Bone only lesions are not suitable for biopsy. Patients undergoing paired biopsies will be assigned into two treatment cohorts (8 in each) and treated according to the schema below.

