### 5.3.2 XL888

The following guidelines are provided for the modification of the dose of XL888 in the event of toxicities attributed by the investigator to this study drug. Toxicities unrelated to XL888 will not ordinarily result in the modification of dose. AEs will be defined based on the National Cancer Institute (NCI) Common Terminology Criteria for Adverse Events (CTCAE) version 4.

In general, subjects experiencing **Grade 1 and 2** drug related toxicities should not have the dose of XL888 modified. However, appropriate supportive care should be provided for the management of drug related toxicities. Grade 2 toxicities may require dose or schedule modifications (delaying or omitting individual doses) due to potentially greater clinical significance; however, this should occur after discussion with study PI. .

Dosing of XL888 must be delayed if a subject experiences a **Grade 3 non-hematologic** toxicity. If the toxicity resolves (returned to baseline or decreased to Grade  $\leq 1$ ) within 14 days, dosing of XL888 may be resumed one lower dose level (See section 5.3.2.1). Exceptions to this rule are as follows:

- Grade 3 fatigue: dose modification are left to the PI's discretion;
- Grade 3 nausea, vomiting and diarrhea: dose modification only after optimal prophylactic measures have failed to control the symptoms adequately;

In the case of Grade 4 **non-hematologic** toxicity, **or persistent Grade 3** toxicity despite one dose level reduction, XL888 will be discontinued.

No dose adjustment of XL888 will be performed for anemia.

No dose adjustment for XL888 will be performed for grade 1, 2, or 3 neutropenia or grade 1, 2, or 3(without bleeding) thrombocytopenia.

Dosing of XL888 will be delayed if subjects develop grade 4 neutropenia or grade 3 thrombocytopenia complicated by bleeding or grade 4 thrombocytopenia. If the toxicity resolves (returned to baseline or decreased to Grade  $\leq 1$ ) within 14 days, dosing of XL888 may be resumed one lower dose level (See section 5.3.2.1).

Dose escalation back to the starting dose will not be allowed.

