#### **7.1.4.2 Treatment Period**

##### **7.1.4.1 Day 1 ( $\pm 3$ days) of each cycle**

- Record concomitant medications
  - Vitals (temperature, HR, BP and RR)
  - History and physical exam, pill diary (prior cycle see section 11.4) and pill count (prior cycle)
  - ECOG performance status
  - Toxicity assessment
  - 12 lead ECG after XL888 administration in cycle 1, cycle 2 and every other cycle
    - Laboratory Assessments

- Hematology hemoglobin, hematocrit, red blood cell count, white blood cell count with differential and platelet count
  - Chemistry sodium, potassium, chloride, bicarbonate, magnesium, calcium, phosphorus, blood urea nitrogen, creatinine, glucose (random), total bilirubin, LDH, total protein, ALP, ALT, AST, and albumin
  - Tumor markers - when applicable
  - Fasting Lipid profile every 3 cycles starting Cycle 4 (i.e C4D1, C7D1, C10D1, C13D1 etc)
  - Urinalysis every 3 cycles starting Cycle 4 (i.e C4D1, C7D1, C11D1 etc)
    - T3, FT4, TSH cycle 2 and then after every 3 cycle
    - For the cycle 1 day 1 labs, blood samples from the screening tests maybe used if completed within 1 week of day 1
- Blood sample 20 cc for correlative work (only cycle 1, 2, 3)
  - Pembrolizumab 200 mg will be administered as a 30 minute IV infusion every 3 weeks. Given the variability of infusion pumps, a window of -5 minutes and +10 minutes is permitted (i.e., infusion time is 30 minutes: -5 min/+10 min).
- XL888 will be administered orally in the infusion center (first dose of each cycle only) prior to pembrolizumab. **(in selected case in patients receiving paired biopsies XL888 will be held in cycle 1)**

#### 7.1.4.2 Days 4, 8, 11, 15 and 18

- XL888 dose administered and diary completed

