#### **7 Calendar-Day Telephone or Fax Report**

The Sponsor-Investigator is required to notify the FDA of a fatal or life-threatening adverse event that is unexpected and assessed by the investigator to be possibly related to the use of *investigational agents*. An unexpected adverse event is one that is not already described in the most recent Guidance for Investigator section of the Investigator's Brochure. Such reports are

to be telephoned or faxed to the FDA, Merck and Exelixis within 7 calendar days of the first learning of the event.

15 Calendar-Day Written Report

The Sponsor-Investigator is also required to notify the FDA and all participating investigators, in a written IND Safety Report, of any serious unexpected adverse event that is considered reasonably or possibly related to the use of investigational agent.

Written IND Safety Reports with analysis of similar events are to be submitted to the FDA, Exelixis, and Merck within 15 calendar days of first learning of the event. The FDA prefers these reports on a MedWatch 3500 Form but alternative formats (eg, summary letter) are acceptable.

FDA Fax number of IND Safety Reports: [name]

All written IND Safety Reports submitted to the FDA by the Sponsor-Investigator must also be faxed to:

Exelixis Drug Safety  
[contact]

Merck Global Safety  
[contact]

Table 6 Evaluating Adverse Events

An investigator who is a qualified physician, will evaluate all adverse events as to:

V4.0 CTCAE Grading	Grade 1	Mild; asymptomatic or mild symptoms; clinical or diagnostic observations only; intervention not indicated.
	Grade 2	Moderate; minimal, local or noninvasive intervention indicated; limiting age-appropriate instrumental ADL.
	Grade 3	Severe or medically significant but not immediately life-threatening; hospitalization or prolongation of hospitalization indicated; disabling; limiting self-care ADL.
	Grade 4	Life threatening consequences; urgent intervention indicated.
	Grade 5	Death related to AE
Seriousness	A serious adverse event is any adverse event occurring at any dose or during any use of investigational product that:	
	†Results in death; or	
	†Is life threatening; or places the subject, in the view of the investigator, at immediate risk of death from the event as it occurred (Note: This does not include an adverse event that, had it occurred in a more severe form, might have caused death.); or	

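### The DLT list has no line for a symptomatic Grade 4 or fatal treatment-related hematologic event other than neutropenia or thrombocytopenia

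*Combined protocol and SAP*

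**What the plan says.** Section 5.2.3 limits DLTs to listed events that are "definitely treatment related adverse events during the first 21 days of therapy". The lines are:

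- prolonged Grade IV neutropenia, or neutropenic fever or sepsis;
- Grade III thrombocytopenia with significant bleeding, or any Grade IV thrombocytopenia;
- nausea, vomiting and diarrhea, in two lines by grade;
- "Other non-hematologic treatment-related toxicity at Grade III or higher";
- a laboratory line that begins "Grade 4 asymptomatic laboratory abnormalities that last for more than 24 hours" and also takes in asymptomatic Grade 3 values lasting more than 21 days;
- "In ability to take more than 75% of XL888 due to toxicity".

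Section 2.0 defines the MTD as a dose at which "less than one-third of the subjects experience a DLT in the first 4 weeks of treatment". Section 5.2.2 stops or lowers the dose at two or more DLTs in 3 or 6 patients. Section 8.2 (Stopping Rules) is marked not applicable. On anemia, section 5.3.2 says "No dose adjustment of XL888 will be performed for anemia". Table 6 describes Grade 4 as "Life threatening consequences; urgent intervention indicated".

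**The concern.** The list ranks events the wrong way round. A Grade 4 hemoglobin value without symptoms that lasts more than a day is a DLT. The same abnormality with symptoms, or one that kills the patient, is on its face not a DLT, because the laboratory line requires the absence of symptoms and the general line excludes hematologic toxicity.

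The dose decision rests on the DLT count in cohorts of 3 to 6, so one event can settle it. The accepted dose is then given in a 32-patient expansion (section 8.1). No separate rule for deaths fills the gap.

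**Working it through.** **Step 1. Test the event against each line of section 5.2.3.** Take a symptomatic Grade 4 or a Grade 5 anemia or hemolysis, definitely treatment related and inside the window.

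| Line | Met directly? | Reason |
|---|---|---|
| Neutropenia, neutropenic fever or sepsis | No | different event |
| Thrombocytopenia | No | different event |
| Nausea, vomiting, diarrhea (both lines) | No | gastrointestinal only |
| General Grade III or higher | No | non-hematologic only |
| Laboratory | No | asymptomatic only |
| XL888 intake | Only indirectly | depends on missed XL888 doses |

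Two indirect routes remain: another listed DLT that accompanies the event (for example a Grade III or higher non-hematologic complication), or the intake line.

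**Step 2. When can the intake line catch it?** The line gives no denominator, so both periods in the protocol are tried. Section 5.2.3 uses 21 days and section 2.0 uses four weeks. XL888 is taken on day 1 and on "Days 4, 8, 11, 15 and 18", which makes six doses in 21 days. Four weeks adds days 22 and 25, making eight. The line is met when the share taken is not more than 75%. All doses before the stop are assumed taken in full.

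| Period | Last dose taken | Share taken | DLT by this line? |
|---|---|---|---|
| 21 days | day 11 | 4/6 = 66.7% | yes |
| 21 days | day 15 | 5/6 = 83.3% | no |
| 4 weeks | day 15 | 5/8 = 62.5% | yes |
| 4 weeks | day 18 | 6/8 = 75.0% | yes |
| 4 weeks | day 22 | 7/8 = 87.5% | no |

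An event that first stops dosing on days 16 to 21 (21-day reading) or days 23 to 28 (4-week reading) cannot meet the line.

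Counting milligrams at the 90 mg level gives the same answer for a late stop: 5 × 90 = 450 of 6 × 90 = 540 mg, or 83.3%. An early reduction to 60 mg can meet the line: 90 + 5 × 60 = 390 of 540 mg, or 72.2%. For non-fatal anemia, however, section 5.3.2 directs no XL888 adjustment, so this route may never open.

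**Step 3. Effect on the decision.** Suppose six patients include one counted DLT and one event of this kind.

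- Counted: 2/6 = 33.3%, which is not below one-third, so the dose is rejected.
- Not counted: 1/6 = 16.7%, which is below one-third, so the dose is accepted.

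**Step 4. Scale, on assumed rates only.** Let p be the per-patient DLT probability. Under the usual 3+3 rule, a level passes with probability (1−p)³ + 3p(1−p)² × (1−p)³. At an assumed counted rate of 20% this is 0.512 + 0.384 × 0.512 = 0.709. If further, mutually exclusive events of this kind occurred at 1%, 2%, 5% or 10% and were counted, the level would pass with probability 0.687, 0.665, 0.600 or 0.494. These rates are assumptions and not estimates for XL888 with pembrolizumab.

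**The case against.** The strongest reply is that the gap is narrow. To escape, an event must be hematologic but neither neutropenia nor thrombocytopenia, Grade 4 or 5, symptomatic, definitely related, inside the window, free of any accompanying listed DLT, and not caught by the intake line. A life-threatening anemia with no Grade III cardiac, respiratory or renal component is unusual. The XL888-001 and XL888-IST1 safety results that can be read in section 4.1.2 do not point to anemia or hemolysis. This stands as an argument about frequency, and it is why no change in acceptance probability is claimed.

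A second reply is oversight. Deaths and other serious events reach the sponsor within 24 hours (section 7.2.3), the study team reviews the event logs, and the DSMC must approve escalation after an update on the relevant safety data (sections 5.2.2 and 10.5). That could block the step from 45 to 90 mg after an uncounted death. It does not alter the count, and it is tied to escalation. Accepting 90 mg, the top level, involves no further escalation, and the plan does not expressly require DSMC approval to open the expansion.

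A third reply is that the no-adjustment rule names only anemia, so hemolysis could lead to XL888 being held. Section 5.3 tells investigators to modify both agents when attribution is unclear. That is fair for early events. It does not help with late ones, or with an event clearly attributed to pembrolizumab, where section 5.3 lets XL888 continue.

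Finally, an investigator might class hemolysis or a death as non-hematologic, since the term is undefined. Whether a fatal event counts should not turn on that choice.

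**Conclusion.** The concern holds. Read literally, section 5.2.3 can leave a life-threatening or fatal treatment-related hematologic event out of the count that sets the dose. One such event can reverse the decision, from 2/6 to 1/6, when exactly one other DLT is present. The finding assumes that the list is exhaustive as worded, that no other listed DLT accompanies the event, and that the intake line is not met. How often this would happen cannot be derived from the documents, and partial safeguards exist. It is therefore a change that should be made, but not a flaw that invalidates the design.

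**What to change.** Add one line to section 5.2.3: *Any Grade 5 event, and any symptomatic Grade 4 hematologic event not listed above, that meets the treatment-relatedness standard of this section is a DLT.* Leave the neutropenia, thrombocytopenia and asymptomatic laboratory lines as they are.

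The cost is a single line of text. The downside is that a rare cohort may have to expand or stop when it would otherwise have passed, which is a reasonable response to a life-threatening or fatal related event. The line keeps the definite-relatedness requirement, so a death judged only possibly related would still not count.

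### The DLT list classifies a brief asymptomatic Grade 3 laboratory event two ways, and its 21-day duration limit cannot be resolved inside the 21-day DLT window

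*Combined protocol and SAP*

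**What the plan says.** Section 5.2.3 defines a DLT as "any of the following definitely treatment related adverse events during the first 21 days of therapy" and lists seven bullets, any one of which is enough. Four of them matter here:

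- First bullet: "Grade IV neutropenia lasting more than 8 days; any neutropenic fever or sepsis".
- Fourth bullet: "Other non-hematologic treatment-related toxicity at Grade III or higher". It has no minimum duration and no exception for laboratory findings.
- Fifth bullet (the laboratory bullet): "Grade 4 asymptomatic laboratory abnormalities that last for more than 24 hours or Grade 3 asymptomatic laboratory abnormalities lasting more than 21 days".
- Last bullet: "In ability to take more than 75% of XL888 due to toxicity".

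Section 2.0 gives a different window. It defines the MTD by the share of subjects who "experience a DLT in the first 4 weeks of treatment".

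Under Section 5.2.2, two or more patients with a DLT among 3 or 6 stop the trial at 45 mg, or move it from 90 mg down to 60 mg. Fewer than two at 45 mg lead to 90 mg. Section 10.5 requires DSMC approval for escalation.

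**The concern.** The fourth and fifth bullets overlap for non-hematologic laboratory tests and give opposite answers for short events. No sentence says which prevails. The fifth bullet also sets a duration as long as the observation window itself, without saying whether the window limits when an event starts or when the criterion must be met.

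The DLT count decides whether to stop, escalate or reduce, and so it decides the recommended phase 2 dose, which is the primary objective. Two investigators who apply the text in good faith could count the same patients differently. The event type is plausible for this drug: Section 5.3.2.2 B reports Grade 3 AST increases in 4 of 33 subjects (12.1%) in study XL888-001.

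**Working it through.** The plan has no figure of its own to reproduce here. The check compares the bullets and then counts days and doses.

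**1. Classification.** Take definitely related, asymptomatic events in the window that cost fewer than two XL888 doses.

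| Event | Literal list: any bullet suffices | Specific bullet overrides the general one |
|---|---|---|
| Grade 3 AST, 10 days | DLT (fourth bullet) | Not a DLT (fifth bullet) |
| Grade 4 non-hematologic laboratory value, 24 hours or less | DLT (fourth bullet) | Not a DLT (fifth bullet) |
| Grade 4 neutropenia, 5 days, no fever or sepsis | DLT (fifth bullet) | Not a DLT (first bullet) |

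On the literal reading, the duration limits in the laboratory bullet do nothing for non-hematologic tests, because every Grade 3 or 4 event already counts. That makes an exception the likelier intent.

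**2. Duration against the window.** For onset on day d and a window ending on day W, the longest duration seen is W − d + 1 days counted inclusively, or W − d elapsed days.

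- W = 21, d = 1: 21 inclusive or 20 elapsed. More than 21 is never reached.
- W = 28 (Section 2.0): d = 7 gives 22 inclusive and d = 8 gives 21, so onset must be by day 7. In elapsed days, d = 6 gives 22 and d = 7 gives 21, so onset must be by day 6.
- Window applied to onset, d = 21: day 42 is the 22nd inclusive day. In elapsed days, 21 are complete on day 42 and the limit is passed only after it. Classification can therefore come three weeks after the window closes.

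**3. What the 75% XL888 criterion catches.** Doses fall on days 1, 4, 8, 11, 15 and 18 (Sections 7.1.4.1 and 7.1.4.2), six in all. Taking 4 of 6 (67%) is a DLT under either reading; taking 5 of 6 (83%) is not. For toxicity attributed to XL888, Section 5.3.2 says "Dosing of XL888 must be delayed if a subject experiences a" Grade 3 non-hematologic toxicity, with resumption one level lower. The table in Section 5.3.2.1 has no level below 45 mg. At 45 mg:

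- found after the day-8 dose: 3/6 = 50%, a DLT either way;
- found before the day-15 dose: 4/6 = 67%, a DLT either way;
- found after the day-15 dose: 5/6 = 83%, so the readings diverge;
- found at the cycle 2 day 1 visit, which the ±3-day window allows on days 19 to 21: 6/6, so the readings diverge.

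At 90 mg, an event found after the day-8 dose with XL888 resumed at 60 mg on day 15 gives 5/6 = 83% by count but (3×90 + 2×60)/(6×90) = 390/540 = 72% by amount. The bullet does not say which measure applies.

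**4. Effect on a decision.** Suppose two of three patients at 45 mg have such an AST rise, first seen at the day-15 draw. Each result arrives after that day's dose, only the day-18 dose is missed, and the event resolves in 10 days. The literal list gives 2/3, so the trial stops. The exception reading gives 0/3, so it goes to 90 mg.

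**The case against.** The strongest reply is that the list already shows its intent. The word Other in the fourth bullet can mean toxicity without a bullet of its own. Otherwise the 72-hour limit on Grade III nausea, vomiting or diarrhea would be pointless and the separate Grade IV bullet redundant. Onset is also the natural sense of events during a period, and other criteria need it: neutropenia starting on day 15 has only 7 inclusive days by day 21, so it could never exceed 8. Section 5.3.2.2 B discontinues XL888 when hepatic dysfunction has not reversed after 3 weeks of interruption, which suggests that 21 days is a deliberate persistence threshold. Section 7.1.5 follows events above Grade 1 to resolution. The DSMC sees the safety data for the dose level before escalation.

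Most of this stands as evidence of intent. It does not remove the problem. Neither precedence nor onset is written, and the opening of the list points the other way. If both are granted, the Grade 3 laboratory criterion can still be undecided when the cohort decision falls due, and no section says to wait. DSMC approval adds oversight but supplies no rule for which reading applies.

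**Conclusion.** Section 5.2.3 is internally inconsistent as written. Read literally, the laboratory bullet's limits have no effect for non-hematologic tests. Read as an exception, its Grade 3 limit cannot be met inside the window, and under an onset window it can stay open until day 42 or just after. The DLT count, and so the dose decision, can differ between readings. Severity is minor to should-fix. The intent can be guessed and the case is probably uncommon, but the rule sits in the primary endpoint.

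Three stronger conclusions are tempting and not supported.

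- A reader might infer a probability of a wrong decision from the 4/33 AST figure. Let b be the rate of other DLTs, r the rate of Grade 3 AST events and s the share of those that escape the 75% criterion. The chance of accepting a dose is q³ + 3pq²·q³ with q = 1 − p. The literal list has p = 1 − (1 − b)(1 − r), and the exception reading has p = 1 − (1 − b)(1 − r(1 − s)). With b = 10% and r = 4/33, the gap is 0 at s = 0, 0.805 − 0.689 = 0.116 at s = 0.5, and 0.906 − 0.689 = 0.217 at s = 1. The answer depends mainly on s, which the documents do not give. The 4/33 pools all dose levels of a study whose MTD was 135 mg. It is not limited to related, asymptomatic or first-cycle events.
- A reader might think that divergence at 45 mg is confined to day-15 findings. The cycle 2 day 1 visit window shows otherwise.
- A reader might conclude that 21 days must be shortened, for example to 7. Nothing in the documents supports that figure. It would make Grade 3 anemia of more than 7 days a DLT, although Section 5.3.2 makes no XL888 adjustment for anemia.

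**What to change.** Make three changes in Section 5.2.3:

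1. Add to the fourth bullet: *except asymptomatic laboratory abnormalities, which are judged by the next criterion*. Exclude neutropenia and thrombocytopenia from the laboratory bullet, because the first two bullets judge them.
2. State that the DLT window applies to onset for every criterion with a duration (24 hours, 72 hours, 8 days, 21 days). Use one window length, since Section 2.0 gives 4 weeks.
3. State either that the cohort decision waits until any pending Grade 3 laboratory event is classified, or that one still unresolved at the decision counts as a DLT.

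Keep 21 days unless the sponsor chooses a shorter limit.

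The cost is a few words in two bullets and two sentences. Waiting can occasionally delay a cohort decision, by up to about three weeks for an event starting on day 21. Counting unresolved events avoids the delay but makes the DLT count slightly more conservative. Section 5.3.2.2 B already requires weekly transaminases for XL888-related rises; other tests may need a repeat draw to time the event.
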